# **12 REPORTING REQUIREMENTS**

These guidelines will be followed for the recording and reporting of adverse events and SAEs.

- 1. Baseline events will be recorded in the medical history section of the case report form (CRF) and will include the terminology event name, grade and start date of the event.
  - a. Baseline events are any medical condition, symptom, or clinically significant lab abnormality present before the informed consent form (ICF) is signed.
    - i. Hematologic laboratory abnormalities will not be recorded as baseline events for patients with acute leukemia, myelodysplastic syndrome, chronic lymphocytic leukemia, or chronic myeloid leukemia in blast phase.
    - ii. If exact start date is unknown, month and year or year may be used as the start date of the baseline event.
- 2. The maximum grade of the adverse event will be captured per course of protocol defined visit date.
- 3. These adverse events will be recorded in the case report form:
  - a. Any grade adverse event that is possibly, probably or definitely related to the study drugs(s).
  - b. All serious adverse events regardless of attribution to the study drug(s).
  - c. Any grade adverse event regardless of attribution to the study drug(s) that results in any dose modification.
- 4. Hematologic adverse events will not be recorded or reported for studies in patients with acute leukemia, myelodysplastic syndrome, chronic lymphocytic leukemia, or chronic myeloid leukemia in blast phase except for:
  - a. Prolonged myelosuppression as defined by the NCI-CTCAE criteria specific for leukemia, e.g., marrow hypocellularity on day 42 or later (≥6 weeks) from start of therapy without evidence of leukemia (<5% blasts), or that results in dose modifications, interruptions or meets the protocol definition of DLT or SAE.
- 5. SAEs will be reported according to institutional policy.
- 6. Protocol specific language regarding the recording and reporting of adverse and serious adverse events will be followed in the event of discordance between the protocol and Leukemia Department-specific adverse event recording and reporting guidelines.

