# Laboratory effects

In the SECURE trial, elevated liver transaminases (alanine aminotransferase (ALT) or aspartate aminotransferase (AST)) >3 x the upper limit of normal (ULN) were reported at the end of study treatment in 4.4% of patients who received isavuconazonium sulfate. Elevations of liver transaminases >10 x ULN developed in 1.2% of patients who received isavuconazonium sulfate.

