# 4.1.2 Secondary

- 4.1.2.1 To evaluate the incidence of IA within 100 days of beginning isavuconazole prophylaxis in newly diagnosed patients with AML/MDS receiving intensive chemotherapy or other therapies.
- 4.1.2.2 To evaluate the incidence of other IFIs within 100 days of beginning isavuconazole prophylaxis in newly diagnosed patients with AML/MDS receiving intensive chemotherapy or other therapies.
- 4.1.2.3 To evaluate the composite outcome of treatment success vs. failure in this patient population (Definition of treatment failure: occurrence of proven or probable IFI, receipt of any other systemic antifungal agent for ≥4 days for suspected IFI, occurrence of an AE possibly or probably related to the study drug resulting in discontinuation of treatment, or withdrawal from the study with no additional follow-up).
- 4.1.2.4 To measure the overall survival (OS) of study participants.
- 4.1.2.5 To measure the IFI-free survival of study participants.
- 4.1.2.6 To document the time to death from any cause in the study population.
- 4.1.2.7 To document the time to death related to IFI in the study population.
- 4.1.2.8 To document the time to diagnosis of proven or probable IFI in the study population.
- 4.1.2.9 To document the time to initiation of empiric anti-fungal therapy in the study population.
- 4.1.2.10 To characterize the safety, tolerability and AE profile of isavuconazole in the prophylactic setting.

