# 4.2.2 Secondary

- 4.2.2.1 Incidence of IA within 100 days of isavuconazole prophylaxis initiation.
- 4.2.2.2 Incidence of other IFIs within 100 days of isavuconazole prophylaxis initiation.
- 4.2.2.3 Rates of treatment success vs. failure (defined above).
- 4.2.2.4 Overall survival.
- 4.2.2.5 Survival without proven or probable IFI.
- 4.2.2.6 Time to death from any cause.
- 4.2.2.7 Time to death related to IFI.
- 4.2.2.8 Time to diagnosis of proven or probable IFI.
- 4.2.2.9 Time to first use of empiric antifungal therapy.
- 4.2.2.10 AEs throughout the duration of isavuconazole prophylaxis until 30 days after the last dose of study drug.

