# 8 EVALUATION DURING STUDY

- 8.1 Complete history and physical examination including ECOG performance status, vital signs, and weight at study drug initiation and every 3 weeks (±1 week) thereafter during the study.
- 8.2 CBC and differential at least 1-2 times per week (differential not required if total WBCs  $\leq 0.5 \times 10^9$ /L).
- 8.3 CMP (defined below in study calendar) at least weekly.
- 8.4 EKG on day 10.
- 8.5 Blood cultures if patient develops fever (oral temperature  $\geq 100.4$  °F or 38 °C sustained over a 1-hour period or a single oral temperature measurement of  $\geq 101$  °F or 38.3 °C).
- 8.6 Chest x-ray (CXR) if patient develops neutropenic (ANC <500/mm^3) fever or any sign or symptom of pulmonary infection (lungs or sinus).
- 8.7 CT scan of the chest (± sinus) within 3 (±1) days of development of neutropenic fever or any sign or symptom of respiratory infection. If positive for infection, CT chest (±sinus) needs to be repeated 2 weeks after institution of therapeutic antimicrobials and then as per physician discretion until resolution of the infection.
- 8.8 Iron staining of bone marrow at the time of response assessment for AML/MDS. Failure to perform this will not be considered a protocol deviation or violation.
- 8.9 Plasma isavuconazole levels on day 8 and day 15 just prior to dosing.
- 8.10 Antimicrobial susceptibility testing of fungal isolates from any IFIs that may develop during the course of the study.
- 8.11 Patients that come off therapy will continue follow-up for toxicity (clinic visit or telephone interview) for 30 days (+/- 5 days) after the end of therapy. At the end-of-study visit, patients will have a physical examination, including recording of vital signs, weight and assessment of ECOG performance status, a CBC, CMP, and AE evaluation.
- 8.12 All study participants will be given a study drug diary to keep a log of each dose of study drug taken, the time the dose was taken, and any missed doses along with the reason for missing the dose, as well as doses that may be vomited up.

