# Analysis Plan

The primary endpoint is the incidence of proven or probable invasive fungal infections (IFI). The IFI rate will be estimated along with the exact 95% confidence interval.

Secondary endpoints include incidence of IA, overall survival, and time to diagnosis of IFI, etc. Descriptive statistics will be used to summarize all secondary endpoints. The incidence rates of binary secondary endpoints will be estimated, along with the exact 95% confidence intervals. The probabilities of time-to-event outcomes (such as time to death) will be estimated using the method of Kaplan and Meier. Log-rank tests will be used to compare the time-to-event outcomes among subgroups of patients.

Subjects who entered the study and did not take any study drug will not be evaluated for safety. The severity of the toxicities will be graded according to the NCI CTCAE v4.0 whenever possible. We will follow standard reporting guidelines for adverse events. Safety data will be summarized by category, severity and frequency. The proportion of patients with AEs will be estimated among all patients.

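### The adverse-event endpoint and its planned proportion carry no attribution limit, but the case report form takes only related, serious or dose-modifying events, so the reported rate is a filtered one under an unqualified label.

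*Combined protocol and SAP*

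**What the plan says.** - **Objective 4.1.2.10:** "To characterize the safety, tolerability and AE profile of isavuconazole in the prophylactic setting".
- **Endpoint 4.2.2.10:** "AEs throughout the duration of isavuconazole prophylaxis until 30 days after the last dose of study drug". It has no condition on relatedness, seriousness or dose change.
- **Section 11, Analysis Plan:** "The proportion of patients with AEs will be estimated among all patients". Safety data are also to be summarised by type, severity and frequency. No laboratory analysis is named.
- **Section 12, item 3:** three routes lead to the CRF. Route 3a depends on the judged cause: "Any grade adverse event that is possibly, probably or definitely related to the study drugs(s"). The other two do not: 3b takes every SAE whatever its cause, and 3c does the same for events that change the dose, in the words "Any grade adverse event regardless of attribution to the study drug(s) that results in any dose modification".
- **Section 12, item 4:** hematologic events are left out in this population, apart from prolonged myelosuppression and the other listed exceptions.
- **Section 8.3:** "CMP (defined below in study calendar) at least weekly". The study calendar lists ALT, AST, alkaline phosphatase and total bilirubin in that panel.
- **Section 2.10, laboratory effects:** liver risk in an earlier treatment trial (SECURE) is described by cut-offs that need no attribution: 4.4% above 3x ULN at the end of treatment, and "Elevations of liver transaminases >10 x ULN developed in 1.2% of patients who received isavuconazonium sulfate".

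**The concern.** The endpoint names one set of events and the data collection supplies a smaller one. What decides whether a non-serious event without dose change enters the data is the investigator's view of its cause.

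That view is hard to form here. There is no control arm. Every patient has AML or MDS and receives chemotherapy or other therapy, and may also be in another therapeutic trial (5.1.1). Concomitant medications go in the medical record and not in the CRF (Section 8), so the judgement cannot be rechecked from the trial data.

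The liver shows the problem most clearly. Section 2.9.1 warns of hepatic reactions, patients may enter with raised transaminases, and AML treatment offers another explanation for a rise. The trial collects objective liver values at least weekly, yet the plan makes no use of them. A reader of the results could take a filtered rate for the rate of all AEs on prophylaxis.

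**Working it through.** The plan states no expected AE or liver rate, so there is no figure to reproduce. The check is to trace events through the recording rules.

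**1. A grade 3 ALT rise, non-serious, no dose change, under different judgements**

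| Circumstance | Route | On CRF? |
|---|---|---|
| Judged at least possibly related | 3a | Yes |
| Judged unrelated, but prolongs hospitalization (an SAE) | 3b | Yes |
| Judged unrelated, but leads to a dose modification | 3c | Yes |
| Judged unrelated, non-serious, no dose modification | none | No |

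The last row is an AE under 4.2.2.10 and is missing from the data behind the Section 11 proportion. Item 4 plays no part in it, because the event is not hematologic; it is a second filter that removes most hematologic AEs.

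**2. Direction of the effect.** Let A be the number of patients with any AE in the endpoint window, R the number with at least one AE that passes items 3 and 4, and N the common denominator. Every patient counted in R is also counted in A, so R ≤ A and R/N ≤ A/N. The recorded proportion can match the all-cause proportion but cannot exceed it.

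**3. Where the loss falls.** One recorded event is enough to count a patient, so the overall proportion loses only patients all of whose events were filtered out. In a table by type of event, a patient is lost from the liver row whenever that patient's liver events were filtered out, whatever else was recorded. The rows by type and grade are therefore at least as exposed as the overall figure.

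**4. Size.** A − R depends on the share of events judged not even possibly related that are also non-serious and without dose change. The documents do not give this share, so no number follows.

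**5. Does other text close the gap?**
- Section 12 item 6 gives protocol language precedence over departmental guidelines. Section 12 is itself protocol text, and 4.2.2.10 does not say what is to be recorded, so nothing is overridden.
- Section 13 says all data go into PDMS/CORE. That may make the panel values available, but it specifies no analysis of them.
- AE evaluation in Section 8 and the calendar is not filtered. The restriction applies at entry to the CRF, which is the source for the analysis.

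**6. Can existing samples fill the liver part?** The calendar schedules the panel before study, in each of weeks 1 to 12, and off study. On treatment this is enough for a maximum value per patient. After treatment it is thin: there is one off-study panel, and that contact may be by telephone. Criterion 5.1.5 allows AST/ALT up to 5x ULN and bilirubin up to 3x ULN at entry. Since 5 > 3, a patient can exceed the 3x ULN transaminase cut-off before the first dose, so a plain count of maxima above 3x ULN would mix baseline abnormality with on-treatment change.

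**The case against.** The strongest reply is that the filter is mild. *Possibly* is a low threshold, and with hepatic reactions named in the protocol's own warnings, few investigators would call a liver rise not even possibly related. Every SAE and every dose-modifying AE is captured regardless of cause. This stands as a limit on the likely loss, but nothing in the plan measures that loss.

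A second reply is that the objective concerns the profile of isavuconazole, and in one arm on chemotherapy an all-cause rate overstates the drug's share. This also stands in part: neither rate is the drug effect. It is a reason to name the rate correctly and show both kinds of figure, not to leave the attributed rate unlabelled. Restricted recording is a legitimate economy if the endpoint says so.

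Three stronger readings are tempting and are not supported:
- *A numerical shortfall.* A reader might start from the 17.1% (44/257) with elevated liver tests in the Section 2.10 table and apply an assumed share judged related. The share would be invented, and the sum would ignore unrelated events caught by routes 3b and 3c.
- *Loss of a direct comparison with that 17.1%.* The table is headed as treatment-emergent reactions, but the document does not show how cause was handled. The figure includes gamma-glutamyltransferase, which this trial's panel does not list, and it comes from treatment of mold infection rather than prophylaxis. Section 11 plans no such comparison.
- *Objective 4.1.2.10 is wholly unmet.* Related, serious and dose-modifying events are all recorded, so much of the profile is available.

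**Conclusion.** The mismatch holds in the current text. Followed as written, the plan reports the proportion of patients with at-least-possibly-related, serious or dose-modifying AEs, mostly without hematologic events, and calls it the proportion with AEs. Against all-cause AEs it can only be equal or too low. The amount cannot be derived from the documents and may be small. Objective 4.1.2.10 is met in part. The missing part is non-serious events without dose change that are attributed elsewhere, and for the liver the trial already draws the samples that would supply it.

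The conclusion rests on two readings: that the CRF is the source of the Section 11 safety summary, and that no text elsewhere requires other AEs to be recorded. I found none. It concerns the safety endpoint and its analysis, not the toxicity stopping rule. The change is worth making because it alters what the safety analysis reports and costs little.

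**What to change.** 1. **Name the subset.** In 4.2.2.10 and the Analysis Plan, describe the endpoint and proportion as *drug-related (at least possibly), serious or dose-modifying AEs, excluding hematologic AEs except as in Section 12 item 4*.

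2. **Add a liver table regardless of attribution**, from the panels already drawn, with exact 95% confidence intervals:
   - the number of patients whose maximum on-treatment ALT or AST exceeds 3x ULN and 10x ULN;
   - shifts from baseline to worst CTCAE grade for ALT, AST, alkaline phosphatase and total bilirubin.

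   Present the cut-off counts by baseline value, or restrict them to patients below the cut-off at baseline, because of criterion 5.1.5. Include the off-study panel where it exists, and note that post-treatment values are sparse.

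**Cost.** A few lines of analysis-plan wording, and transfer of existing laboratory results into the analysis data. No new visit, sample, patient or clinical rule is needed. The liver figures will include chemotherapy effects and will look less favourable than attributed rates, and the report must say so. For AEs with no laboratory measure, the fix corrects the label but does not recover the unrecorded events.

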#### Serious Adverse Event Reporting (SAE) for M. D. Anderson-Sponsored IND Protocols

An adverse event or suspected adverse reaction is considered "serious" if, in the view of either the investigator or the sponsor, it results in any of the following outcomes:

- Death
- A life-threatening adverse drug experience any adverse experience that places the patient, in the view of the initial reporter, at immediate risk of death from the adverse experience as it occurred. It does not include an adverse experience that, had it occurred in a more severe form, might have caused death.
- Inpatient hospitalization or prolongation of existing hospitalization
- A persistent or significant incapacity or substantial disruption of the ability to conduct normal life functions.
- A congenital anomaly/birth defect.

Important medical events that may not result in death, be life-threatening, or require hospitalization may be considered a serious adverse drug experience when, based upon appropriate medical judgment, they may jeopardize the patient or subject and may require medical or surgical intervention to prevent one of the outcomes listed in this

definition. Examples of such medical events include allergic bronchospasm requiring intensive treatment in an emergency room or at home, blood dyscrasias or convulsions that do not result in inpatient hospitalization, or the development of drug dependency or drug abuse (21 CFR 312.32).

- Important medical events as defined above, may also be considered SAEs. Any important medical event can and should be reported as an SAE if deemed appropriate by the Principal Investigator or the IND Sponsor, IND Office.
- All events occurring during the conduct of a protocol and meeting the definition of a SAE must be reported to the IRB in accordance with the timeframes and procedures outlined in "The University of Texas M. D. Anderson Cancer Center Institutional Review Board Policy for Investigators on Reporting Unanticipated Adverse Events for Drugs and Devices". Unless stated otherwise in the protocol, all SAEs, expected or unexpected, must be reported to the IND Office, regardless of attribution (within 5 working days of knowledge of the event).
- All life-threatening or fatal events, that are unexpected, and related to the study drug, must have a written report submitted within 24 hours (next working day) of knowledge of the event to the Safety Project Manager in the IND Office.
- Unless otherwise noted, the electronic SAE application (eSAE) will be utilized for safety reporting to the IND Office and MDACC IRB.
- SAEs will be captured from the time of the first protocol-specific intervention, until 30 days after the last dose of drug, unless the participant withdraws consent. SAEs must be followed until clinical recovery is complete and laboratory tests have returned to baseline, progression of the event has stabilized, or there has been acceptable resolution of the event.
- Additionally, any SAEs that occur after the 30 day time period that are related to the study treatment must be reported to the IND Office. This may include the development of a secondary malignancy.

#### **Reporting to FDA:**

• SAEs will be forwarded to FDA by the IND Sponsor (Safety Project Manager IND Office) according to 21 CFR 312.32.

It is the responsibility of the PI and the research team to ensure that SAEs are reported according to the Code of Federal Regulations, Good Clinical Practices, the protocol guidelines, the sponsor's guidelines, and Institutional Review Board policy.

#### **Investigator Communication with Supporting Companies:**

These reports will also be submitted to Astellas safety by email at: [contact]

#### **Reporting of External SAEs**

The MDACC institutional policy for reporting of external SAEs will be followed.

#### **13 CONFIDENTIALITY PLAN**

All data will be entered in PDMS/CORE.

January 12, 2017 2016-0373

